8.3.2. Baseline Characteristics

For the primary objective of characterizing RRMM patients treated with belantamab mafodotin per routine clinical care, data at the time of the first belantamab mafodotin dose (i.e., the index date) or from the initial MM diagnosis until the index date (i.e., the

baseline period) will be collected retrospectively or at study enrolment, where applicable. Data to be collected are shown in [Table 2](#).

Table 2 Demographics, disease and treatment history

Item	Variable	Definition	Timing
Demographics	Date of birth	Year of birth	Index date
	Sex	Categorical variable: 
 • Male • Female 	Index date
	Height	Continuous variable	Index date
	Weight	Continuous variable	Index date
	ECOG Performance Status	Categorical variable: 
 • 0 • 1 • 2 • 3 • 4 	Index date
MM History	Date initial diagnosis	Date of first MM diagnosis	Baseline period
	Extramedullary disease	Categorical variable	Baseline period
	ISS stage	Categorical variable: stage at initial MM diagnosis 
 • I • II • III 	Baseline period
	MM subtype	Categorical variable: subtype at initial diagnosis 
 • IgG • IgA • IgM • IgD • Biclonal (G,A) • Light chain MM • Other 	Baseline period
	Cytogenetic risk	Categorical variable: 
 • High [e.g., t(4;14), t(14;16), del17p] • Standard 	Baseline period
	Progression status	Categorical variable: disease progression (per IMWG criteria or to local standard practice) on last line of therapy: 
 • Yes • No 	Baseline period
	Refractory status	Categorical variable: 
 • Triple refractory • Quad refractory • Penta refractory 	Index date

Item	Variable	Definition	Timing
MM Treatment History	Prior MM therapies	Categorical variable: therapy type* by line per EHA-ESMO (Dimopoulos, 2021) and NCCN guidelines (Kumar, 2020)	Baseline period
	Dates of prior MM therapies	Date of first and last dose of each prior therapy	Baseline period
Medical History	Pre-existing comorbidities	Categorical variable: type of comorbidity** per category such as: 
 • Renal diseases • Pulmonary diseases • Cardiac diseases • Diabetes • Eye diseases including history of dry eye/eye injuries affecting the BCVA • Other 	Baseline period
Ophthalmic Health	BCVA	Continuous variable per type of measurement	Baseline period
	Slit lamp exam	Categorical variable: most recent corneal examination finding: 
 • Keratopathy • Microcyst-like epithelial changes • Other corneal findings/ conditions 	Baseline period
Laboratory measurements	Lactate dehydrogenase, creatinine	Continuous variables: based on most recent assessments: 
 • Lactate dehydrogenase • Serum creatinine • Creatinine clearance using the Cockcroft-Gault formula 	Baseline period

Abbreviations: BCVA=Best Corrected Visual Acuity, ECOG=Eastern Cooperative Oncology Group; EHA=European Hematology Association; ESMO= European Society for Medical Oncology; Ig=Immunoglobulin; IMWG=International Myeloma Working Group; ISS=International Staging System; NCCN=National Comprehensive Cancer Network.

*The World Health Organization (WHO) Drug Dictionary for medications will be used for coding drugs.

**The Medical Dictionary for Regulatory Activities (MedDRA) will be used for coding concomitant diseases.

8.3.3. Belantamab Mafodotin Treatment

Belantamab mafodotin treatment data to be collected during follow-up from standard of care visits are shown in [Table 3](#). Data will be collected from the time of the first belantamab mafodotin dose until permanent discontinuation of belantamab mafodotin treatment, the end of follow-up at 15 months, study discontinuation for any reason, informed consent withdrawal or death; whichever comes first.

Table 3 Belantamab mafodotin treatment

Variable	Definition	Timing
Date(s) of Administration	Date of each administration	Index date and post-index treatment period
Dose	Continuous variable: prescribed and administered doses	Index date and post-index treatment period
Treatment status change	Categorical variable: prospectively captured or derived retrospectively 
 • Dose modification • Treatment interruption / delay • Discontinued 	Post-index treatment period
Primary reason dose modification	Categorical variable: 
 • Any AE • Other 	Post-index treatment period
Primary reason treatment interruption/delay	Categorical variable: 
 • Any AE • Patient decision unrelated to AEs • Other 	Post-index treatment period
Primary reason treatment discontinuation	Categorical variable: 
 • Disease progression • Any AE • Patient decision unrelated to AEs • End of treatment • Death (unrelated to therapy) • Other 	Post-index treatment period
Concomitant Medications	Categorical variable: type of concomitant medication* Continuous variable: dose at index date for each concomitant medication	Index date and post-index treatment period

Abbreviations: AE=adverse event.

8.3.4. Ophthalmic Monitoring

As part of the key secondary objectives, ophthalmic monitoring information (Table 4) will be collected during follow-up from standard of care visits from the time of the first belantamab mafodotin dose until permanent discontinuation of belantamab mafodotin treatment, the end of follow-up at 15 months, study discontinuation for any reason, informed consent withdrawal or death; whichever comes first.

Table 4 Ophthalmic Monitoring

Variable	Definition	Timing
Date(s) ophthalmic examination(s)	Date of each examination	Index date and post-index treatment period
Type(s) of ophthalmic examination(s)	Categorical variable: 
 • BCVA score (Snellen test or equivalent test) • Slit lamp examination • Other 	Index date and post-index treatment period
Result of Examination	Categorical variable, result for each eye: 
 • BCVA score (continuous variable) • Corneal examination findings: 
 • No change • Mild superficial keratopathy • Moderate superficial keratopathy • Severe superficial keratopathy • Corneal epithelial defect /ulcer KVA scale grade for worst eye (see ANNEX 2): 
 • Normal • Grade 1 • Grade 2 • Grade 3 • Grade 4 	Index date and post-index treatment period
Use of contact lenses while on treatment*	Categorical variable: 
 • Yes – specify use • No 	Index date and post-index treatment period
Use of preservative-free lubricant eye drops while on treatment	Categorical variable: 
 • Yes – specify use • No 	Index date and post-index treatment period
Use of bandage contact lenses while on treatment	Categorical variable: 
 • Yes – specify use • No 	Index date and post-index treatment period
Use of cooling eye masks	Categorical variable: 
 • Yes – specify use • No 	Index date and post-index treatment period

Abbreviations: BCVA=best Corrected Visual Acuity; KVA=Keratopathy and Visual Acuity.

*Patients should avoid using contact lenses until the end of treatment unless directed by an ophthalmologist.

8.3.5. Safety

All ocular AESIs that occur during and/or after administration of belantamab mafodotin will be recorded regardless of a causal relationship to belantamab mafodotin. Data shown in [Table 5](#) will be collected for any ocular AESI (serious or non-serious) until the end of follow-up at 15 months, study discontinuation for any reason, informed consent withdrawal or death; whichever comes first.

Table 5 Ocular Adverse Events of Special Interest

Variable	Definition	Timing
Date(s) ocular AESI(s)	Date of onset of each ocular AESIs	Index date and post-index period
Ocular AESI type	Categorical variable: type of ocular AESI* categorized by: 
 • Keratopathy** • Blurred vision events# • Dry eye events## • Photophobia • Eye irritation • Ulcerative keratitis • Infective keratitis • Corneal erosion/defect • Other 	Index date and post-index period
Ocular AESI severity at onset	Categorical variable: NCI CTCAE Version 5.0 grading: 
 • Grade 1 • Grade 2 • Grade 3 • Grade 4 • Grade 5 KVA scale grade (see ANNEX 2): 
 • Normal • Grade 1 • Grade 2 • Grade 3 • Grade 4 	Index date and post-index period
Ocular AESI severity increase after onset	Categorical variable: 
 • Yes – specify highest grade • No 	Index date and post-index period
Ocular AESI seriousness at onset	Categorical variable: 
 • Fatal • Life-threatening • Persistent or significant disability/incapacity • Inpatient (or prolongation of existing) hospitalization • Medically important event • None of the above 	Index date and post-index period
Ocular AESI seriousness increase after onset	Categorical variable: 
 • Yes – specify most serious event • No 	Index date and post-index period
Ocular AESI impact on daily living	Categorical variable (e.g., need for caregiver support, eye irritation/pain, driving impairment, reading impairment)	Index date and post-index period
Action taken	Categorical variable: 
 • Concomitant medication@ and other mitigation strategies (e.g., bandage contact lenses) • Belantamab mafodotin treatment change 
 • Dose decrease • Treatment interruption/delay 	Index date and post-index period

	
 • Treatment discontinuation • Change in ophthalmic monitoring • Withdrawn from study • No action taken 	
Documented relationship to belantamab mafodotin	Categorical variable: 
 • Yes • No • Unknown 	Index date and post-index period
Ocular AESI outcome	Categorical variable: 
 • Fatal • Not recovered/not resolved • Recovered/resolved • Resolved with sequelae • Recovering/resolving • Unknown 	Index date and post-index period Please refer to Section 10
Ocular AESI stop date, if applicable	Date of ocular AESI resolution	Post-index period

Abbreviations: AESI=adverse event of special interest; KVA=Keratopathy and Visual Acuity; NCI CTCAE=National Cancer Institute Common Terminology Criteria for Adverse Events.
*MedDRA will be used for coding AEs. **Based on eye examination, characterised as corneal epithelium changes with or without symptoms. #Includes diplopia, vision blurred, visual acuity reduced and visual impairment. ##Includes dry eye, ocular discomfort, and eye pruritus @The WHO Drug Dictionary for medications will be used for coding drugs.

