Continuous variables will be described (distribution) by their mean, standard deviation, median, first and third quartile (Q1 and Q3), extreme values (minimum and maximum) and the number of non-missing and missing data. Categorical variables will be described using frequency counts and percentages.

Data analysis:

The following measures will be reported:

- Exposure-adjusted incidence and event rates with 95% confidence intervals of ocular AESIs (i.e., at the patient level and the event level): overall and by SOC and PT terms (MedDRA classification).
- Median, 95% confidence intervals (CIs) and 25th and 75th percentiles using the Kaplan-Meier (KM) method for time to event outcomes (i.e., OS, rwPFS, DoR, time to discontinuation, time to first [specific] ocular AESI)
- OS rates with 95% CIs at specified time points, including 12- and 15-months of follow-up
- Overall response rate (ORR) with 95% CIs calculated based on the exact binomial distribution (Clopper-Pearson method).

Additional subgroup analyses will be conducted for primary and secondary outcomes by key patient characteristics (e.g., Eastern Cooperative Oncology Group [ECOG] performance status, age groups at the index date, MM subtype, retrospective vs prospective data, and presence or absence of ocular AESIs) when deemed applicable and feasible, as described in the Statistical Analysis Plan (SAP).

Details of interim analyses will be described in the SAP.

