8.7.2.3. Analysis of Key Secondary Objectives

For the key secondary objectives, the following will be described for the SP (overall and by line of treatment) during active treatment exposure periods:

- Average cycle dose (sum of all doses divided by total number of administrations per patient)
- Frequency and timing of ophthalmic monitoring relative to belantamab mafodotin administration for each cycle (type(s), number of examinations; overall and according to monitoring before and after the occurrence of ocular AESIs as well as treatment dose and frequency)
- Ocular AESIs in RRMM patients exposed to belantamab mafodotin occurring during the study period:
 - Number, proportions, co-occurrence and time to (specific) ocular AESIs; overall and by System Organ Class (SOC) and Preferred Term (PT) terms (MedDRA classification) and according to severity, grade, seriousness, action taken, duration, impact on daily living and relationship to treatment as well as treatment dose and frequency
 - Number, proportion, severity, grade, seriousness and duration of ocular AESIs by ophthalmic monitoring frequency, type(s) and timing relative to administration
 - Severity, grade, seriousness and duration of ocular AESIs by their treatment impact (e.g., dose changes, duration of interruptions/delays, discontinuation), use of artificial tears and dry eye comorbidity

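### Time to ocular AESIs is planned by severity, grade and seriousness, but Table 5 does not date a worsening, so time to the highest CTCAE grade or seriousness cannot be derived for events that worsen

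*Protocol*

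**What the plan says.** **Planned output.** Under the key secondary objectives, Protocol Section 8.7.2.3 lists "Number, proportions, co-occurrence and time to (specific) ocular AESIs". The same bullet asks for these "and according to severity, grade, seriousness, action taken, duration, impact on daily living and relationship to treatment". A further bullet asks for "Severity, grade, seriousness and duration of ocular AESIs by their treatment impact". The abstract (Section 3.9) repeats these items and names, among the Kaplan-Meier outcomes, "time to first [specific] ocular AESI". The text does not say whether a breakdown by severity uses the grade at onset or the highest grade.

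**Collected data.** For each ocular AESI, Table 5 (Section 8.3.5) lists:
- the "Date of onset of each ocular AESIs";
- the CTCAE and KVA grade at onset;
- whether severity later increased, with the entry "Yes – specify highest grade";
- seriousness at onset and, in the same yes/no form, any later increase;
- one stop date, for resolution of the event.

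Table 5 has no date for an increase in severity or seriousness.

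**Second source.** Table 4 (Section 8.3.4) records dated eye examinations with BCVA, corneal findings and KVA grade. These run only until permanent discontinuation of belantamab mafodotin or the end of follow-up, and contain neither CTCAE grade nor seriousness.

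**The concern.** The form anticipates that an AESI may worsen and records how far, but not when. A time-to-event analysis by severity needs the date on which the severity was reached. For an event that starts mild and becomes severe, the only start date in Table 5 belongs to the mild phase.

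The type, duration and severity of ocular AESIs form part of the key secondary objective (Section 7.2), and the study also describes monitoring visits relative to dosing. If severe events are placed at the onset of their mild phase, they look as though they arise earlier in treatment than they do. The SAP can choose which grade defines the tables, but it cannot supply a date that is not collected.

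**Working it through.** The protocol states no figure on this point, so there is nothing to reproduce. The check sets outputs against dated fields and then shows the size of the error with assumed dates.

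**Step 1: which outputs can be derived?**

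| Output | Dates needed | Available? |
|---|---|---|
| Time to first (specific) AESI | onset | yes, Table 5 |
| Time to onset, by grade at onset | onset | yes, Table 5 |
| Duration of the whole event | onset, resolution | yes, Table 5 |
| Number and proportion by highest grade | none | yes, Table 5 |
| Time to highest grade, examination-based event, on treatment | date of worsening | approximately, from Table 4 examinations |
| Time to highest CTCAE grade of a symptom (dry eye, photophobia) that worsened | date of worsening | no |
| Time to highest seriousness, if increased | date of increase | no |
| Time to highest grade, worsening after permanent discontinuation | date of worsening | no |

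**Step 2: size for one event.** Let onset be day *a* and worsening *k* visits later. Visit spacing is 21 days, from the roughly three-weekly visits assumed in Section 8.3.7.

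- True time to highest grade = *a* + 21*k*.
- Time if the onset date stands in = *a*.
- Error = −21*k* days.

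Assume onset on day 21 and resolution on day 147; neither date is in the documents:

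| Visits from onset to worsening (*k*) | True day of highest grade | Day from Table 5 | Error (days) |
|---|---|---|---|
| 0 | 21 | 21 | 0 |
| 1 | 42 | 21 | −21 |
| 2 | 63 | 21 | −42 |
| 3 | 84 | 21 | −63 |
| 4 | 105 | 21 | −84 |

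Whole-event duration is 147 − 21 = 126 days in every row, and correct. If the highest grade lasted one or two visits (21 or 42 days), reading 126 days as time spent at that grade would overstate it by 105 or 84 days. That is an error of labelling, since time spent at the highest grade is not a planned output.

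**Step 3: size across events.** Mean understatement = *f* × *L*, where *f* is the fraction of events classed at a high grade that began lower and *L* is their mean lag. The documents give neither. With an assumed *L* of 42 days (the middle of one to three cycles), *f* = 0.25, 0.50 and 0.75 give 10.5, 21 and 31.5 days. These values restate the assumptions and do not estimate the error in this study.

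**The case against.** The strongest reply is that the protocol names neither time to highest grade nor duration at highest grade. Its Kaplan-Meier outcome is time to first AESI, which needs only onset. Onset time and whole-event duration are correct even for an event that later worsens, and choosing onset or highest grade for a table is ordinary SAP content. Table 4 also covers much of the ground: keratopathy is defined by eye examination, reduced visual acuity can be followed through BCVA, and corneal defects appear among the graded findings. Interruptions and delays fall within its window. Dosing dates in Table 3 can be lined up with these examinations.

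Most of this stands, and it rules out three stronger readings that a reader might infer:
- That severe events are given a wrong duration. They are not; the planned duration is that of the event.
- That severe events will be counted too rarely. Nothing says the tables use grade at onset, and the highest grade is recorded.
- That the bias has a known percentage. Any such figure depends on an invented worsening rate and lag.

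The reply does not remove the narrower gap. Section 8.7.2.3 asks for time to AESI by severity, grade and seriousness, and on a natural reading by highest level that cannot be produced for symptoms graded by CTCAE or for seriousness. The gap after permanent discontinuation matters less if the analysis is confined to active treatment exposure periods, as the lead-in to that section says. The AESI item itself refers to the wider study period, and Table 5 collects events throughout follow-up.

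It is also fair that dates from routine visits will be approximate. A date accurate to the visit is still better than the onset date of a milder phase.

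**Conclusion.** The point holds in a limited form. For an AESI that worsens after onset, Table 5 does not allow time to its highest CTCAE grade or seriousness to be derived, although the plan breaks time to AESI down by these attributes. Table 4 closes the gap for examination-based events on treatment. It does not do so for CTCAE-graded symptoms, seriousness, or worsening after permanent discontinuation.

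The error arises only if events are classed by highest level and dated by onset. It then equals the lag from onset to worsening: 21 to 84 days for lags of one to four visits, on the assumed spacing. Its average size in this study is unknown. This is a low-cost improvement to data collection; it does not invalidate the safety analysis.

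**What to change.** - Add to Table 5 the date on which the highest grade was first reached and, separately, the date on which the highest seriousness was first reached, each completed only when an increase is recorded.
- Define time to an AESI of grade *k* or higher as the onset date if the onset grade is already at least *k*, and otherwise as the new date. For an event that passes through *k* on its way to a higher grade, the new date is a latest possible value; if exact times to intermediate grades are wanted, each grade change needs a date.
- State whether each severity table uses the grade at onset or the highest grade.
- Label any duration tabulated by highest grade as the duration of the whole event.

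The cost is one or two date fields on the AESI page, taken from notes the site already reads to enter the highest level, with no added visit or procedure. Dates will be approximate to the visit, and some will be missing in retrospective records.

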8.3.6. Effectiveness

Table 6 shows the effectiveness data to be collected during the study period from the time of the first belantamab mafodotin dose until the end of follow-up at 15 months, study discontinuation for any reason, informed consent withdrawal or death; whichever comes first.

Table 6 Effectiveness

Variable	Definition	Timing
Date of death	Date of death	Post-index period
Tumour response	Assessment dates and categorical variable per IMWG response criteria (IMWG, 2021 Criteria) if feasible or to local standard practice: 
 • sCR • CR • VGPR • PR • No change/stable disease • PD 	Post-index period

Abbreviations: CR=complete response IMWG=International Myeloma Working Group; PD=Progressive disease; PR=partial response; sCR=stringent complete response; VGPR; very good partial response.

8.3.7. Timings of Assessment

Data will be collected from patients' visits per routine clinical care either prospectively, directly into the eCRF or retrospectively from data already available in medical records into the eCRF (Table 7).

Table 7 Data Collection Plan

Variables	Baseline period	Standard of Care Visits*
Informed Consent	X	
Patient Eligibility	X	
Subject Characteristics	X	
Medical/Treatment History	X	
Concomitant Medications	X	X
Belantamab Mafodotin Treatment	X	X
Ophthalmic Monitoring and Results**	X	X
Ocular AESIs#	X	X
Effectiveness Evaluations		X

Abbreviations: AESI=adverse event of special interest.

*Data will be collected only if reported as part of standard of care visits, which are assumed to take place about every three weeks during treatment in accordance with local treatment guidelines until the end of follow-up. ** In the EU, eye examinations are required before the first three treatment cycles. Additional eye examinations are required promptly as clinically indicated (e.g., on worsening of ocular symptoms (BLNREP SmPC, 2021). #Other AEs and serious adverse events (SAEs) will not be actively solicited and based on spontaneous reporting.

8.4. Data Sources

Data will be collected by Investigators or their designees (i.e., haematologists, oncologists and ophthalmologists) for all patients enrolled into this study from sites in elected countries across Europe. Countries and sites in Europe will be included based on the expected belantamab mafodotin market uptake and site availability.

Baseline and outcome data will be extracted retrospectively from medical records or entered prospectively directly into the eCRF, where applicable.

8.5. Study Size

Approximately 150 evaluable RRMM patients are planned for the study. The sample size is not based on statistical power consideration but on a conservative estimate for each country of interest based on country-specific MM incidence and prevalence rates, the percentage of patients expected to be eligible for belantamab mafodotin treatment, the expected belantamab mafodotin market uptake, site availability and the treatment landscape in terms of ongoing clinical trials.

The sample size 150 RRMM patients from EU sites is considered sufficient to meet the primary objective of describing RRMM patients treated with belantamab mafodotin per

routine clinical care in terms of demographics, disease status, clinical characteristics and treatment history.

To meet the planned number of 150 evaluable RRMM patients, the enrolment period may be extended if needed based on the actual uptake of belantamab mafodotin and site participation. Eligible RRMM patients from sites who received their first belantamab mafodotin dose before study enrolment will be invited for study participation if this is deemed necessary based on the enrolment rate in the EU. The number of patients who received their first belantamab mafodotin dose before study enrolment is expected to be low as belantamab mafodotin was either only recently launched or is in the process of being launched.

